5.2.2 Enzalutamide

Enzalutamide Dose Modification Levels

Dose reduction levels	enzalutamide
(starting dose)	160 mg/day
-1	120 mg/day
-2	80 mg/day

Hepatic Toxicity

For \geq Grade 2 ALT or AST or Bilirubin (see Investigations in CTCAE v. 5.0), treatment days should be skipped for grade 2 related toxicities and restarted at the original dose level once recovered to grade \leq 1. If the same toxicity recurs at \geq grade 2, interrupt enzalutamide. Restart enzalutamide at one dose level reduction when ALT, AST, and bilirubin recover to Grade 1. Discontinue enzalutamide therapy IF toxicity recurs after two dose reductions or does not improve to grade 1 or lower within 28 days of onset of adverse event.

For hepatic failure (see Hepatobiliary Disorders in CTCAE v. 5.0), discontinue enzalutamide.

Neurologic toxicity

Discontinue enzalutamide for any seizure.

Reversible posterior leukoencephalopathy syndrome (RPLS)

For signs and symptoms suggestive of reversible posterior leukoencephalopathy syndrome (RPLS) such as confusion, headache, seizures, and cortical blindness, hold enzalutamide for up to 4 weeks. Suspected RPLS should be investigated with MRI. If diagnosis of RPLS is confirmed, enzalutamide should be permanently discontinued. If RPLS is ruled out via MRI and signs and symptoms attributed to another cause, enzalutamide should resume.

Hypersensitivity

Discontinue enzalutamide.

Ischemic Heart Disease

Optimize management of cardiovascular risk factors. Discontinue enzalutamide for Grade 3-4 events.

Falls and Fractures

Falls and fractures occurred in 10% and 8% of patients receiving enzalutamide, respectively. Evaluate patients for fracture and fall risk, and treat patients with bone-targeting agents according to established guidelines.

Other Non-Hematologic Grade 3 or 4 Toxicity

For patients who experience a Grade 3 or greater toxicity attributed to enzalutamide, enzalutamide should be held for one week or until symptoms improve to \leq Grade 2. Patients may be re-started on enzalutamide at the same or one dose level reduction. If treatment is held for more than 4 weeks, discontinue protocol therapy.

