1.4 Other Agents

Enzalutamide (standard of care as monotherapy)

Enzalutamide is an androgen receptor antagonist which acts by competitively inhibiting (1) testosterone binding to androgen receptors, (2) nuclear translocation of androgen receptors, and (3) DNA binding and activation by androgen receptors. Enzalutamide was approved by the FDA in 2012 for the treatment of men with mCRPC who have progressed on or after first-line docetaxel chemotherapy. In September 2014, the FDA expanded the use of enzalutamide to include men with CRPC that have not received prior chemotherapy.

Clinical Trial Experience

Because clinical trials are conducted under widely varying conditions, adverse reaction rates observed in the clinical trials of a drug cannot be directly compared to rates in the clinical trials of another drug and may not reflect the rates observed in practice.

Three randomized clinical trials enrolled patients with metastatic prostate cancer that has progressed on androgen deprivation therapy (GnRH therapy or bilateral orchiectomy), a disease setting that is also defined as metastatic CRPC. Two trials were placebo-controlled (Studies 1 and 2), and one trial was bicalutamide-controlled (Study 3). In Studies 1 and 2, patients received enzalutamide 160 mg or placebo orally once daily. In Study 3, patients received

enzalutamide 160 mg or bicalutamide 50 mg orally once daily. All patients continued androgen deprivation therapy.

Patients were allowed, but not required, to take glucocorticoids.

The most common adverse reactions ($\geq 10\%$) that occurred more commonly ($\geq 2\%$ over placebo) in the enzalutamide- treated patients from the two randomized placebo-controlled clinical trials were asthenia/fatigue, back pain, decreased appetite, constipation, arthralgia, diarrhea, hot flush, upper respiratory tract infection, peripheral edema, dyspnea, musculoskeletal pain, weight decreased, headache, hypertension, and dizziness/vertigo.

Study 1: Enzalutamide versus Placebo in Metastatic CRPC Following Chemotherapy

In this study of patients with metastatic CRPC who had previously received docetaxel, the median duration of treatment was 8.3 months with enzalutamide and 3.0 months with placebo. During the trial, 48% of patients on the enzalutamide arm and 46% of patients on the placebo arm received glucocorticoids.

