Grade 3 and higher adverse reactions were reported among 47% of enzalutamide-treated patients and 53% of placebo- treated patients. Discontinuations due to adverse events were reported for 16% of enzalutamide-treated patients and 18% of placebo-treated patients. The most common adverse reaction leading to treatment discontinuation was seizure, which occurred in 0.9% of the enzalutamide-treated patients compared to none (0%) of the placebo-treated patients.

Table 1 shows adverse reactions reported in Study 1 that occurred at a $\geq 2\%$ higher frequency in the enzalutamide arm compared to the placebo arm.

Table 1. Adverse Reactions in Study 1

	Enzalutamide N = 800		Placebo N = 399	
	Grade 1-4 ^a (%)	Grade 3-4 (%)	Grade 1-4 (%)	Grade 3-4 (%)
General Disorders				
Asthenic Conditions ^b	50.6	9.0	44.4	9.3
Peripheral Edema	15.4	1.0	13.3	0.8
Musculoskeletal And Connective Tissue Disorders				
Back Pain	26.4	5.3	24.3	4.0
Arthralgia	20.5	2.5	17.3	1.8
Musculoskeletal Pain	15.0	1.3	11.5	0.3
Muscular Weakness	9.8	1.5	6.8	1.8
Musculoskeletal Stiffness	2.6	0.3	0.3	0.0
Gastrointestinal Disorders				
Diarrhea	21.8	1.1	17.5	0.3
Vascular Disorders				
Hot Flush	20.3	0.0	10.3	0.0
Hypertension	6.4	2.1	2.8	1.3
Nervous System Disorders				
Headache	12.1	0.9	5.5	0.0
Dizziness ^c	9.5	0.5	7.5	0.5
Spinal Cord Compression and Cauda Equina Syndrome	7.4	6.6	4.5	3.8
Paresthesia	6.6	0.0	4.5	0.0
Mental Impairment Disorders ^d	4.3	0.3	1.8	0.0
Hypoesthesia	4.0	0.3	1.8	0.0
Infections And Infestations				
Upper Respiratory Tract Infection ^e	10.9	0.0	6.5	0.3
Lower Respiratory Tract And Lung Infection ^f	8.5	2.4	4.8	1.3
Psychiatric Disorders				
Insomnia	8.8	0.0	6.0	0.5
Anxiety	6.5	0.3	4.0	0.0
Renal And Urinary Disorders				
Hematuria	6.9	1.8	4.5	1.0
Pollakiuria	4.8	0.0	2.5	0.0
Injury, Poisoning And Procedural Complications				
Fall	4.6	0.3	1.3	0.0
Non-pathologic Fractures	4.0	1.4	0.8	0.3
Skin And Subcutaneous Tissue Disorders				
Pruritus	3.8	0.0	1.3	0.0
Dry Skin	3.5	0.0	1.3	0.0

	Enzalutamide N = 800		Placebo N = 399	
	Grade 1-4 ^a (%)	Grade 3-4 (%)	Grade 1-4 (%)	Grade 3-4 (%)
Respiratory Disorders				
Epistaxis	3.3	0.1	1.3	0.3
a CTCAE v5.0				
b Includes asthenia and fatigue.				
c Includes dizziness and vertigo.				
d Includes amnesia, memory impairment, cognitive disorder, and disturbance in attention.				
e Includes nasopharyngitis, upper respiratory tract infection, sinusitis, rhinitis, pharyngitis, and laryngitis.				

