f Includes pneumonia, lower respiratory tract infection, bronchitis, and lung infection.				

Study 2: Enzalutamide versus Placebo in Chemotherapy-naïve Metastatic CRPC

Study 2 enrolled 1717 patients with metastatic CRPC who had not received prior cytotoxic chemotherapy, of whom 1715 received at least one dose of study drug. The median duration of treatment was 17.5 months with enzalutamide and 4.6 months with placebo. Grade 3-4 adverse reactions were reported in 44% of enzalutamide-treated patients and 37% of placebo-treated patients. Discontinuations due to adverse events were reported for 6% of enzalutamide-treated patients and 6% of placebo-treated patients. The most common adverse reaction leading to treatment discontinuation was fatigue/asthenia, which occurred in 1% of patients on each treatment arm. Table 2 includes adverse reactions reported in Study 2 that occurred at a \geq 2% higher frequency in the enzalutamide arm compared to the placebo arm.

Table 2. Adverse Reactions in Study 2

	Enzalutamide N = 871		Placebo N = 844	
	Grade 1-4 ^a (%)	Grade 3-4 (%)	Grade 1-4 (%)	Grade 3-4 (%)
General Disorders				
Asthenic Conditions ^b	46.9	3.4	33.0	2.8
Peripheral Edema	11.5	0.2	8.2	0.4
Musculoskeletal And Connective Tissue Disorders				
Back Pain	28.6	2.5	22.4	3.0
Arthralgia	21.4	1.6	16.1	1.1
Gastrointestinal Disorders				
Constipation	23.2	0.7	17.3	0.4
Diarrhea	16.8	0.3	14.3	0.4
Vascular Disorders				
Hot Flush	18.0	0.1	7.8	0.0
Hypertension	14.2	7.2	4.1	2.3
Nervous System Disorders				
Dizziness ^c	11.3	0.3	7.1	0.0
Headache	11.0	0.2	7.0	0.4
Dysgeusia	7.6	0.1	3.7	0.0
Mental Impairment Disorders ^d	5.7	0.0	1.3	0.1
Restless Legs Syndrome	2.1	0.1	0.4	0.0
Respiratory Disorders				

Dyspnea ^e	11.0	0.6	8.5	0.6
Infections And Infestations				
Upper Respiratory Tract Infection ^f	16.4	0.0	10.5	0.0
Lower Respiratory Tract And Lung Infection ^g	7.9	1.5	4.7	1.1
Psychiatric Disorders				
Insomnia	8.2	0.1	5.7	0.0
Renal And Urinary Disorders				
Hematuria	8.8	1.3	5.8	1.3
Injury, Poisoning And Procedural Complications				
Fall	12.7	1.6	5.3	0.7
Non-Pathological Fracture	8.8	2.1	3.0	1.1
Metabolism and Nutrition Disorders				
Decreased Appetite	18.9	0.3	16.4	0.7
Investigations				
Weight Decreased	12.4	0.8	8.5	0.2
Reproductive System and Breast disorders				
Gynecomastia	3.4	0.0	1.4	0.0

a CTCAE v5.0
 b Includes asthenia and fatigue.
 c Includes dizziness and vertigo.
 d Includes amnesia, memory impairment, cognitive disorder, and disturbance in attention.

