5.2 Toxicities and Dosing Delays/Dose Modifications

Any patient who receives treatment on this protocol will be evaluable for toxicity. Each patient will be assessed for the development of toxicity according to the Time and Events Table (Section 6.4). Toxicity will be assessed according to the NCI Common Terminology Criteria for Adverse Events (CTCAE), version 5.0. Dose adjustments should be made according to the system showing the greatest degree of toxicity.

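### Section 5.2.2 both stops and resumes enzalutamide for a patient with a seizure, an MRI that rules out RPLS and another assigned cause

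*Combined protocol and SAP*

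**What the plan says.** Two adjacent paragraphs of section 5.2.2 govern enzalutamide after a seizure.

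- **Neurologic toxicity:** "Discontinue enzalutamide for any seizure". There is no qualification by cause, grade or work-up.
- **RPLS:** for signs "such as confusion, headache, seizures, and cortical blindness, hold enzalutamide for up to 4 weeks". Suspected RPLS is to be investigated by MRI, and two outcomes are then given. One is "If diagnosis of RPLS is confirmed, enzalutamide should be permanently discontinued". The other is "If RPLS is ruled out via MRI and signs and symptoms attributed to another cause, enzalutamide should resume".

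Neither paragraph refers to the other, and the resume sentence does not exclude patients whose signs included a seizure. The only general rule on conflicting adjustments is in section 5.2: "Dose adjustments should be made according to the system showing the greatest degree of toxicity".

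**The concern.** A seizure brings a patient under both paragraphs. The first ends enzalutamide. The second can put the patient back on it. If both apply and nothing ranks them, one written rule directs re-exposure after a seizure and the rule just above it forbids that. Two sites could each follow the protocol and treat the same patient differently.

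The drug makes this more than a drafting matter. Section 1.4 reports that in Study 1 seizure was the most common adverse reaction leading to discontinuation of treatment, "which occurred in 0.9% of the enzalutamide-treated patients compared to none (0%) of the placebo-treated patients". The branch is also clinically plausible here: section 3.2 does not exclude a history of seizure, and 3.2.10 admits patients with treated, stable brain metastases, to which a seizure might be attributed.

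**Working it through.** The check is a comparison of rules, followed by a bound on how often the case could arise.

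**Rule trace for a patient whose RPLS-suggestive signs include a seizure (5.2.2)**

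| Situation | Seizure paragraph | RPLS paragraph | Final actions agree? |
|---|---|---|---|
| MRI confirms RPLS | Discontinue | Discontinue permanently | Yes |
| MRI rules out RPLS, no other cause assigned | Discontinue | Resume sentence not triggered | No opposite instruction |
| MRI rules out RPLS, another cause assigned | Discontinue | Resume | **No** |

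The first action also differs (discontinue against hold), but the final action conflicts only in the third row.

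**Could discontinue mean a temporary stop?** Not easily. Elsewhere in 5.2.2 temporary stops are called skipping, interrupting or holding. Discontinuation is the word used for hepatic failure and for Grade 3-4 ischemic heart disease.

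**Does other text set precedence?** Section 5.2 ranks organ systems by degree of toxicity, whereas both paragraphs here concern the same neurologic event. Section 5.5 allows treatment to stop for unacceptable adverse events or on the investigator's judgement, but does not say which paragraph of 5.2.2 governs. The monthly data review in section 13.0 may reveal a divergence after the fact; it does not instruct the clinician at the time.

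**How often could it arise?** Inputs:

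- n = 35 planned evaluable patients (section 11.0).
- Seizure rate p. The only seizure figure in the documents is the 0.9% of Study 1, which counts seizures leading to discontinuation. It comes from a different population: "In this study of patients with metastatic CRPC who had previously received docetaxel". This trial excludes prior chemotherapy for metastatic castration-resistant disease (3.2.1).
- A closer population is described by "Study 2 enrolled 1717 patients with metastatic CRPC who had not received prior cytotoxic chemotherapy", but no seizure rate is given for it. Its table covers only reactions at least 2% more frequent on enzalutamide, so the absence of seizure from that table gives no estimate.

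I therefore assume p between 0.1% and 0.9%. The two lower values have no source in the documents. Expected seizures = n × p; chance of at least one = 1 − (1 − p)^n.

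| Assumed p | Expected seizures | Chance of at least one |
|---|---|---|
| 0.1% | 35 × 0.001 = 0.035 | 1 − 0.999^35 = 0.034 |
| 0.5% | 35 × 0.005 = 0.175 | 1 − 0.995^35 = 0.161 |
| 0.9% | 35 × 0.009 = 0.315 | 1 − 0.991^35 = 0.271 |

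At each assumed rate this is a ceiling on the conflict, which also needs suspected RPLS, an MRI that rules it out and another assigned cause. The documents do not give the fraction of seizures that meet these conditions.

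**The case against.** The strongest reply is that the paragraphs can be read together. The seizure rule is absolute; the RPLS paragraph deals only with what to do while RPLS is suspected. On that view the resume sentence lifts the RPLS hold and leaves any other stopping rule in force. Nobody would conclude that a patient with a Grade 3 ischemic event must resume because an MRI excluded RPLS. Seizures are one of several illustrative signs, and listing them as a prompt for MRI makes sense even when the drug is already stopped. Investigators may always stop treatment under 5.5, so the text never compels re-exposure.

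This is a sensible reading and perhaps the intended one, but the protocol does not state it. The opposite reading is also open: the RPLS paragraph is the more specific of the two, it names seizures itself, and its resume instruction is directive. The ischemic comparison is weaker than it looks, because ischemic events are not among the signs that the RPLS paragraph says may be cleared.

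Three parts of the reply stand. The probabilities above are for any seizure, so the conflict is less likely by an unknown amount. The top of the range rests on a rate from another population. And investigator judgement with monthly review makes unnoticed divergence between sites less likely.

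**Conclusion.** The inconsistency is real and the point is minor. Section 5.2.2 gives opposite final actions for one narrow group: patients with a seizure, RPLS ruled out by MRI and another cause assigned. No text settles which applies. That follows from the wording alone and needs no assumption about rates.

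In practice the case may well never occur. The expected number of seizures of any kind is 0.04 to 0.32 under the assumed rates, and only some of those would reach the conflicting branch. The consequence concerns patient safety and uniform dosing. Duration of therapy, a descriptive secondary endpoint, could be affected at most slightly. Neither primary endpoint definition, the TITE-CRM, the PSA success rule nor the sample size depends on it.

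**What to change.** Keep seizure as a trigger for the RPLS work-up, and add to the end of the RPLS paragraph in 5.2.2 a clause such as: except that enzalutamide is not resumed after any seizure. If the clinical team wants to allow resumption when another cause is found, the seizure rule should instead be limited to seizures not attributed to another cause. The choice is clinical; either wording removes the conflict.

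The cost is one clause at the next amendment, with no added visits, data collection or analyses.

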5.3 Concomitant Medications/Treatments

Medications or vaccinations specifically prohibited in the exclusion criteria are not allowed during the ongoing trial. If there is a clinical indication for any medication or vaccination specifically prohibited during the trial, discontinuation from trial therapy or vaccination may be required. The investigator should discuss any questions regarding this with the Study PI. The final decision on any supportive therapy or vaccination rests with the investigator and/or the subject's primary physician. However, the decision to continue the subject on trial therapy or vaccination schedule requires the mutual agreement of the investigator, the Sponsor and the subject.

Use of bisphosphonates/RANKL inhibitors are standard in CRPC and are allowed on the study.

Subjects are prohibited from receiving the following therapies during the Screening and Treatment of this trial:

- Antineoplastic systemic chemotherapy or biological therapy except for ongoing androgen deprivation therapy (e.g. with LHRH agonist/antagonist)
- Immunotherapy
- Chemotherapy not specified in this protocol
- Investigational agents
- 5 α -reductase inhibitors (e.g., finasteride, dutasteride).
- Any herbal product known to decrease PSA levels (eg. Saw Palmetto and PC-SPES)
- Neulasta[®]
- Radiation therapy
 - Local intervention is discouraged unless medically unavoidable. Radiation therapy to a symptomatic solitary lesion/area may be considered on a

case-by-case basis after consultation with the Principal Investigator (except during screening). Subjects receiving local intervention (e.g., palliative radiation) are allowed to continue to receive study treatment at the investigator's discretion. Subjects who receive local intervention may be considered not evaluable (and may be assigned a conservative censoring or progression date).

- Live vaccines within 30 days prior to the first dose of treatment and while participating in the trial. Examples of live vaccines include, but are not limited to, the following: measles, mumps, rubella, varicella/zoster, yellow fever, intranasal influenza, rabies, BCG (tuberculosis vaccine), and typhoid vaccine.
- Systemic glucocorticoids or other immunosuppressive drugs for any purpose other than to modulate symptoms from a drug-related AE of immunologic etiology (refer to Section 5.2 – Dose Modification). The use of physiologic doses of corticosteroids may be approved after consultation with the Study PI.
 - Use of prophylactic corticosteroids to avoid allergic and other adverse reactions (e.g., to IV contrast dye or transfusions) is permitted.
 - Use of intermittent inhaled steroids or local injection of corticosteroids is permitted upon consultation with the Principal Investigator.
 - Physiologic doses of prednisone ≤ 10 mg (or equivalent) per day.
- Avoid strong CYP2C8 inhibitors CYP3A4 inducers as they can increase the plasma exposure to enzalutamide. If co-administration is necessary, reduce the dose of enzalutamide.
- Avoid CYP3A4, CYP2C9, and CYP2C19 substrates with a narrow therapeutic index as enzalutamide may decrease the plasma exposure of these drugs.
- The exclusion criteria describe other medications prohibited in this trial.

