9.2 Enzalutamide

Other names for the drug: XTANDI®

Description:

Enzalutamide is a white crystalline non-hygroscopic solid. Enzalutamide is provided as a liquid-filled soft gelatin capsule for oral administration. Each capsule contains 40 mg of enzalutamide as a solution in caprylocaproyl polyoxylglycerides.

Classification: type of agent: androgen receptor inhibitor

Mode of action:

Enzalutamide is an androgen receptor inhibitor that acts on different steps in the androgen receptor signaling pathway. Enzalutamide has been shown to competitively inhibit androgen binding to androgen receptors and inhibit androgen receptor nuclear translocation and interaction with DNA.

Pharmacokinetics:

Absorption: rapid with time to peak concentration in 1 hour (range 0.5-3 hours). A high-fat meal did not alter the AUC to enzalutamide or N-desmethyl enzalutamide.

Distribution: 110 L; protein binding of parent drug is 97-98% to primarily albumin; protein binding of active metabolite is 95% to plasma proteins

Metabolism: Hepatic via CYP2C8 (formation of active metabolite N-desmethyl enzalutamide) and CYP3A4

Excretion: Primarily eliminated by hepatic metabolism. Following single oral administration of 14C-enzalutamide 160 mg, 85% of the radioactivity is recovered by 77 days post dose: Urine (71%), feces (14%) primarily as inactive metabolite

T1/2: Enzalutamide: 5.8 days (range 2.8-10.2 days); N-desmethyl enzalutamide: 7.8-8.6 days.

Side effects:

The most common adverse reactions ($\geq 10\%$) are asthenia/fatigue, back pain, decreased appetite, constipation, arthralgia, diarrhea, hot flush, upper respiratory tract infection, peripheral edema, dyspnea, musculoskeletal pain, weight decreased, headache, hypertension, and dizziness/vertigo.

Drug Interactions: Please refer to the package insert for enzalutamide.

Storage and stability: Store enzalutamide at 20° to 25°C (68° to 77°F) in a dry place and keep the container tightly closed. Excursions permitted to 15° to 30°C (59° to 86° F).

Administration:

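### Section 5.3 says CYP3A4 inducers raise enzalutamide exposure and calls for a dose cut; the clearance route in section 9.2 implies the opposite

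*Combined protocol and SAP*

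**What the plan says.** The list of restricted therapies in section 5.3 (Concomitant Medications/Treatments) contains this instruction: "Avoid strong CYP2C8 inhibitors CYP3A4 inducers as they can increase the plasma exposure to enzalutamide". No connecting word stands between the two drug classes. The bullet then says: "If co-administration is necessary, reduce the dose of enzalutamide". It does not separate inhibitors from inducers, give the size of the reduction, or refer to the enzalutamide dose steps in section 5.2.2.

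Section 9.2 (Enzalutamide) describes how the drug is handled. Metabolism is given as "Hepatic via CYP2C8 (formation of active metabolite N-desmethyl enzalutamide) and CYP3A4", and under excretion the text reads "Primarily eliminated by hepatic metabolism". Its entry on drug interactions is a referral: "Please refer to the package insert for enzalutamide".

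No other part of the document gives a separate instruction for CYP3A4 inducers.

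**The concern.** The bullet gives two drug classes the same effect and the same action, although on the protocol's own account of clearance they act in opposite directions. An inhibitor reduces an enzyme's activity and an inducer increases it. If both enzymes clear enzalutamide, an inhibitor of one and an inducer of the other cannot both be expected to raise exposure.

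This is a dosing rule that sites are meant to follow, not background text. A patient who must take a CYP3A4 inducer would be expected to have lower enzalutamide exposure because of the inducer, and the bullet would then lower it further by cutting the dose. Enzalutamide is the active partner in the combination. The dose table in section 5.1.2 holds it at 160 mg at all three dose levels, and section 11 treats its dose as fixed. A cut made for a mistaken reason departs from that design, risks under-treating the patient, and adds noise to that patient's PSA response and toxicity data.

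**Working it through.** The plan states no figure on this point and none is claimed here. The check compares the bullet in section 5.3 with the pharmacology in section 9.2.

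**Inputs**

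- Stated effect for both classes (section 5.3): exposure increases.
- Stated action for both classes (section 5.3): reduce enzalutamide.
- Clearing enzymes (section 9.2): CYP2C8 and CYP3A4.
- Main route of elimination (section 9.2): hepatic metabolism.

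The only premise added is the meaning of the terms: an inhibitor lowers enzyme activity and an inducer raises it.

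**Direction for each class**

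| Class | Effect on metabolism | Expected exposure | Section 5.3 says | Consistent? |
|---|---|---|---|---|
| Strong CYP2C8 inhibitor | slower | up | up; reduce dose | yes |
| CYP3A4 inducer | faster | down | up; reduce dose | no, on both effect and action |

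One of the two classes is wrong.

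**Could a lost word explain it?** The gap between the two class names suggests a drafting or text-extraction slip, so the possible repairs need testing.

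1. Restoring *and*, *or* or a slash leaves inducers tied to increased exposure and to the dose cut.
2. A longer phrase lost at the same place leaves the rest of the sentence as it is. Inducers are then the nearest noun for the claim of increased exposure, unless the lost words expressly excluded them.
3. If the author meant CYP3A4 inhibitors, the printed word is wrong and the protocol has no instruction for inducers.

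Each of these readings still needs a correction.

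**Size.** Three quantities would be needed to express the consequence as a number: how many patients need a CYP3A4 inducer, how far exposure falls in them, and how large the dose cut would be. The documents give none of these, nor the share of clearance that runs through CYP3A4. The number of affected patients could be zero.

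**The case against.** The strongest reply is that the bullet is hedged by several safeguards and would rarely, if ever, change what a patient receives.

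- The first instruction is to avoid these drugs, and the bullet sits in a list introduced as prohibited therapies.
- Section 5.3 also says that a clinical need for a prohibited medication may require stopping trial therapy. Questions go to the study's principal investigator, and continuing on trial therapy needs agreement between the investigator, the sponsor and the subject. A site might therefore not cut the dose on its own.
- Section 9.2 sends sites to the package insert for interactions, so a governing source is already named.
- The sentence is visibly garbled, which points to an editing slip rather than a deliberate rule.
- No endpoint, DLT definition or analysis depends on it.

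Most of this stands as a limit on reach. Harm requires a patient with no alternative to the inducer, agreement to continue, and nobody checking the insert. It is also fair to call this a wording error rather than a design decision.

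The reply does not make the bullet correct. The bullet itself provides for necessary co-administration, which is exactly where the error operates. The agreement step decides whether the patient continues; it does not say what to do with the dose, and the bullet does. The package-insert referral is general and sits in another section, while the bullet is explicit. A site that declined to reduce the dose would be departing from the protocol as written. That the slip was accidental is a reason to correct it.

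**Conclusion.** The concern holds. For CYP3A4 inducers, section 5.3 gives the wrong direction of effect and an action that would compound the loss of exposure. For strong CYP2C8 inhibitors the bullet agrees with section 9.2.

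The conclusion rests on the clearance route in section 9.2 and on what induction of a clearing enzyme means. Section 9.2 does not itself state the effect of inducers, so the direction is inferred; no outside figure is used. The effect cannot be quantified, and the error bites only when co-administration is judged necessary. It does not touch the sample size, the dose-assignment rule or the efficacy criterion. It should be corrected as a matter of patient safety.

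**What to change.** Split the bullet in two.

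1. **Strong CYP2C8 inhibitors:** keep the present content. Avoid; exposure may rise; lower enzalutamide if the combination cannot be avoided.
2. **CYP3A4 inducers:** state that they can lower enzalutamide exposure, that they should be avoided, and that their use must not trigger a reduction in enzalutamide. Take any specific dose action for unavoidable use from the package insert to which section 9.2 already refers.

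If the author meant CYP3A4 inhibitors in the present sentence, give them their own line checked against the insert, and still add the line for inducers.

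The cost is one bullet rewritten as two, with no change to design, sample size or analysis.
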